## **5 STUDY ENROLLMENT AND WITHDRAWAL**

### **5.1 Subject Inclusion Criteria**

In order to be eligible to participate in this study, an individual must meet all of the following criteria:

- Age 18 or older
- Able and willing to access the internet on a regular basis
- Able and willing to participate in weekly phone coaching calls
- Able to read and speak English\*\*
- Willing and able to comply with all study procedures and be available for the duration of the study:
- Has a diagnosis of TMD pain using a self-report screener, specifically:
  1. Reporting pain in the jaw or temple area (on either side) in the last 30 days.
  2. Reporting pain or stiffness in the jaw on awakening in the last 30 days.
  3. Reporting changes in pain (either better or worse) in the jaw or temple area (on either side) in the last 30 days, after the following activities: chewing hard or tough food, opening the mouth or moving the jaw forward or to the side, jaw habits such as holding teeth together, clenching/grinding, or chewing gum, or other jaw activities such as talking, kissing, or yawning
- Has a frequency of TMD pain more than once a week with pain in the past 6 months
- Provides an electronically signed and dated informed consent form.

### **5.2 Subject Exclusion Criteria**

An individual who meets any of the following criteria will be excluded from participation in this study:

- Currently participating in any other TMD/TMJ related studies
- Has major disc disorder requiring opioids or is scheduled to have surgery for TMD pain
- Has any serious medical condition that might interfere with or prohibit participation in an online program
- Is pregnant
- Has been treated for a mental health disorder or substance abuse in the past six months

\*\* Note: This project is limited to subjects with the ability to read and speak English since one of the primary outcome instruments (Jaw Functional Limitation Scale) is only validated in English.

### 5.3 Strategies for Recruitment and Retention

Participants will be recruited using two recruitment protocols, which may run in the same clinics:

- A. Recruitment Protocol 1 relies on the participant proactively calling the Survey Research Center (SRC) following receiving information about the study from their dental clinic;
- B. Protocol 2 relies on the SRC initiating contact by sending a letter and making subsequent outbound telephone calls.

All recruitment materials will be submitted to the Institutional Review Boards (IRBs) for review and approval prior to their use.

#### **Recruitment Protocol 1: *Inbound recruitment – Self referral through clinic information***

Pre-implementation:

- A. Clinics will be identified for initial participant recruitment. Clinical directors/ and or managers will be contacted for participation in the study and process of recruitment.
- B. Clinicians at sites will be informed about the study and asked to refer patients with diagnosed TMD to the study, or direct patients to clinic brochures.

Implementation:

- A. Brochures will be placed in clinic waiting rooms or other places staff deemed appropriate
- B. Dentist or hygienist will discuss the study or encourage patients to review the study brochure.
- C. Potential study participant interested in the study will contact the SRC at HPI. The SRC will describe the study and proceed to the phone screening.

#### **Recruitment Protocol 2: *ICD-9/ICD-10 code identification***

Pre-implementation:

- A. Clinics will be identified for initial participant direct recruitment. Clinic medical directors/ and or managers will be contacted to discuss the study and recruitment.
- B. Dental providers will be asked to review recruitment letter that will be sent to their patients identified using ICD-9/ICD-10 codes as having TMD, and to provide approval of use of their signature on the letter.

Implementation:

- A. The study programmer will use the ICD-9/ICD-10 codes for TMD diagnosis (within specified timeframe) to identify all patients in HPDG from [DATE] thru [DATE] eligible for study recruitment. ICD10 codes are M26.6x, G44.209 and M79.x. We will cross check these codes with ICD-9 codes from the past including 524.6x and 729.x
- B. Once a potential participant is identified using ICD-9 / ICD-10 codes for TMD their contact information will be accessed. A weekly list will be generated from a search of the HealthPartners claims data.

- C. Name, address, and primary dental provider will be used to generate recruitment letter with primary dental provider signature.
- D. The potential participants would then be sent an introductory letter signed by the provider and study PI and study brochure inviting participation. The letter will also contain a telephone number to call to decline to participate in, or be contacted about the study.
- E. Participants not declining participation within 1 week of initial recruitment letter will be contacted by the SRC regarding participation in the study.
- F. If after hearing a brief description of the study the potential participant is interested; the SRC will proceed with the phone screen.

### **Compensation:**

Participants will be compensated for their participation in the study in an amount stated in the informed consent.

## **5.4 Assignment Procedures**

### **5.4.1 Randomization Procedures**

Participants will be assigned to a study arm through a computer-generated randomization procedure completed within the programming of the TMD Pain Study website. The ratio between intervention and control arms will be 1:1. Randomization scheme will be prepared by the statistician using a permuted block design. The maintenance of trial randomization scheme will occur within the database of the TMD Pain Study website and reviewed periodically by study coordinator to ensure that concealment has been maintained.

Randomization process will be prepared by the statistician, a member of the Research Methodology Group at Health Partners Institute. The maintenance of trial randomization scheme will occur within the database of the TMD Pain Study website. To ensure that the allocation cannot be predicted by researchers, the algorithm will be based on permuted blocks design of 4 and 2 with a 1:1 allocation ratio. Assignment will be accessed directly through the on-line PACT portal after a participant has completed the consent and baseline survey. The use of the online portal will assure allocation concealment, immediate notification of the assignment to the participants, and access to the assigned program.

### **5.4.2 Masking Procedures**

Since the control and intervention arms of the study are significantly different due to the more extensive training and health coaching in the PACT program, it may be apparent to patients which group they are in. As a result, it is probable that neither the intervention group nor the control group will be completely masked to the group they are in. However, both groups will complete all outcome measures through the web-based system.

The following procedures will be used for blinding and protection from bias. Baseline data are collected prior to randomization. Participants and researchers are not blinded to allocation because of the nature of the study. Participants may share this information with their dental care team. Baseline and follow up data are collected through the online program and transferred to a database format with group assignment indicated,. All reports reviewed by the

PI.

## **5.5 Subject Withdrawal**

Participants may withdraw voluntarily from the study at any time or the investigator may terminate participation for any of the following reasons:

- Participant reports that the TMD self-care practices result in:
  - sustained increased pain,
  - the jaw locks,
  - or if the participant appears to display serious emotional difficulties, dissatisfaction or confusion with care during the lessons.
- Participant refuses to participate in any of the PACT program activities after enrollment.
- Continued participation deemed to be not in the participant's best interest.
- Investigator discretion.

Participants withdrawn after randomization will not be replaced.

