Intervention (adherence/compliance)	
 
1. Number of participants accessing all online lessons
 
2. Use of health coaches (PACT arm)
 
3. Pain and risk assessment instruments within the PACT program (PACT arm)
 
4. Time spent in online program per week (PACT arm)
 
	
 
1. 80% of enrolled participants access all lessons as measured by Web site hits
 
2. 90% of participants in PACT have at least 3 phone meetings with the health coach (PACT arm)
 
3. Completion of all pain and risk assessment instruments within the PACT program (PACT arm)
 
4. Time spent in each module of online program per week (PACT arm)
 

- c. Completion of questionnaires at 8-week and 16-week follow-ups, and program evaluation. Completion of questionnaires will be measured by the percent of participants who complete the 8-week and 16-week follow-up questionnaires and, the program evaluation. We expect that at least 80% of participants will complete all questionnaires.

Objective	Constructs	Target outcomes
Evaluation (adherence/compliance)	
 
1. Number of participants completing 8-week and 16-week follow-up questionnaires
 
2. Number of participants completing the program evaluation survey questions (PACT arm)
 
	
 
1. 80% complete both 8- and 16-week follow-up questionnaires
 
2. 80% of participants in PACT group complete the program evaluation form
 

Evaluation (instrument performance)	
 
1. Responsiveness to constructs in subscales of the survey.
 
2. Inter-correlations between scales
 
3. Participant burden is measured by time to complete.
 
	
 
1. Outcome variables show changes in the expected direction
 
2. Outcome variables are associated with mediator/moderator factors in the expected direction
 
3. 90% of participants complete all surveys in estimated time
 

- d. Participant perceptions of the online website functionality and acceptability will be measured by participant reports of problems and ease of use reported at the program

evaluation. These reports will come from the number of phone calls/questions received about web-site issues, and from the qualitative interview.

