### **5.5.1 Reasons for Withdrawal**

Study staff will record reasons for withdrawal or discontinuation when possible. If the participant withdraws consent, no further evaluations will be performed, and no attempts will be made to collect additional data.

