### **5.5.2 Handling of Subject Withdrawals or Subject Discontinuation of Study Intervention**

Study staff will contact each participant who is withdrawing or discontinuation to discuss and document the reasons for withdrawal or discontinuation. All information will be documented in a log of participant completion of study activities.

Any participant discontinued due to TMD self-care practices resulting in sustained increased pain, the jaw locking, or displaying serious emotional difficulties, dissatisfaction or confusion with care during the lessons will be referred to their HealthPartners Dental Provider for further evaluation and follow-up.

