## **6.4 Final Study Visits (Final Visits, Weeks 8 and 16)**

All participants will be asked to complete the final follow-up outcomes evaluation at 8 weeks from the beginning of the intervention and at 16-weeks (2 months after program end). This includes questions about any adverse events and outcomes as reported by the participants during or after the lessons.

Participants will receive weekly email reminders from the web-system to complete the post-intervention questionnaires. There is a 2-week window in the completion of questionnaires at the 8-week and 16-week post-intervention time periods. If the questionnaire has not been completed at the 2-week period, participants will receive up to 3 reminder calls from the study coordinator to identify the barrier to completing the questionnaires and facilitate its completion.

If after two more weeks of time have passed without completion, the questionnaire will be not evaluable, and therefore, considered missing data.

At the end of the 8 week outcome questionnaire, participants will complete several program evaluation questions. In addition, at least ten randomly-selected subjects will complete a semi-structured qualitative interview about their experience in the program.

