### **6.5 Withdrawal Visit**

If a participant is discontinued before study completion, prior to withdrawal of consent and with the participant's permission, an Early Termination visit will occur. Each of the procedures described for the Final Study Visit will be performed at (specify timeframe).

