### **11.4 Final Analysis Plan**

We will perform the following analysis and present results in preparation of the full study. The Primary outcomes for this study are acceptability and feasibility of the methods. The study is not sufficiently powered to test for mean changes from baseline to follow-up. Thus, we will conduct the following descriptive analysis at noted in the outcome measures:

- Number of participants, baseline characteristics and outcomes at baseline will be summarized descriptively
- Summary measures will include mean values (standard deviation SD) for continuous variables and frequency distribution for categorical variables.
- Outcome measures will be analyzed for departure of normality, and standard transformations will be applied.
- Percent of participants completing the measures for outcomes, mediating and moderating factors at baseline and each follow-up periods

The acceptability of the outcomes, mediating and moderating measures at baseline and follow-up periods

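### Sections 5.5 and 5.5.2 allow removal for apparent dissatisfaction or confusion with care, and no rule says how people removed unrated count in the program-acceptability percentages

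*Protocol*

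**What the plan says.** Section 5.5 gives the investigator permission, not an obligation, to terminate participation. One group of reasons concerns effects of the self-care practices: sustained increased pain, jaw locking, "or if the participant appears to display serious emotional difficulties, dissatisfaction or confusion with care during the lessons". Refusal of program activities, the participant's best interest and investigator discretion are listed separately. People withdrawn after randomisation are not replaced. Section 5.5.2 repeats the ground when it says what happens next: a person discontinued for "displaying serious emotional difficulties, dissatisfaction or confusion with care during the lessons will be referred to their HealthPartners Dental Provider".

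On the outcome, section 11.4 states: "The Primary outcomes for this study are acceptability and feasibility of the methods". The SAP says the same. Ratings of the program come from two sources:

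- The program evaluation. Section 6.4: "At the end of the 8 week outcome questionnaire, participants will complete several program evaluation questions". In the Appendix G survey, item 22a asks about satisfaction with the information and item 22d about whether the material was clear.
- Interviews with at least ten randomly selected participants (7.1.2.2). In the PACT version of the 8-week survey, willingness to be interviewed is asked in item 28, near the end.

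Section 3.2.1, items d and e, sets 90% targets for the website accessibility rating, for interviewees finding the content acceptable, and for interviewees finding the coaches helpful.

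On data after discontinuation, section 5.5.1 says: "If the participant withdraws consent, no further evaluations will be performed, and no attempts will be made to collect additional data". Section 6.4 asks all participants for follow-up. Section 6.5 provides an Early Termination visit, with the participant's permission, and adds: "Each of the procedures described for the Final Study Visit will be performed at (specify timeframe"; the placeholder is still there.

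The single acceptability line in the analysis lists of 11.4 and the SAP concerns the measures. Neither list gives a denominator for program acceptability or a rule for people who were removed.

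**The concern.** A removal rule that overlaps an outcome can select on that outcome. A participant who is visibly dissatisfied or confused in week 3 is a likely source of unfavourable answers to items 22a and 22d. If that person is removed, and neither the evaluation nor the interview question reaches them, the unfavourable view drops out of numerator and denominator together. The percentage among those who remain then describes people who did not show dissatisfaction or confusion strongly enough to be removed.

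Acceptability is one of the two things this pilot must establish before a multi-site trial. With 40 people per arm, one or two individuals move a percentage by several points. Because no denominator is fixed in advance, it could also be chosen after the results are known.

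**Working it through.** The plan states no figure on this point, so there is nothing to reproduce. The documents also give no removal rate. What follows is an illustration.

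**Inputs.** N = 40 in the PACT arm (11.2). S = number truly favourable, assumed. r = unfavourable participants unrated, assumed. f = favourable participants unrated, assumed.

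**Formula.** Percentage among those rated = (S − f) / (40 − r − f). True percentage = S / 40.

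| S | r | f | Among rated | True | Difference (points) |
|---|---|---|---|---|---|
| 35 | 1 | 0 | 35/39 = 89.7% | 87.5% | +2.2 |
| 35 | 2 | 0 | 35/38 = 92.1% | 87.5% | +4.6 |
| 35 | 1 | 1 | 34/38 = 89.5% | 87.5% | +2.0 |
| 35 | 2 | 2 | 33/36 = 91.7% | 87.5% | +4.2 |
| 32 | 1 | 0 | 32/39 = 82.1% | 80.0% | +2.1 |
| 32 | 2 | 0 | 32/38 = 84.2% | 80.0% | +4.2 |
| 35 | 1 | 7 | 28/32 = 87.5% | 87.5% | 0 |

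**Direction.** The figure among those rated is too high only if unfavourable people are over-represented among the unrated, that is if r/(r + f) exceeds (40 − S)/40. With S = 35 the threshold is 5/40 = 12.5%. The last row sits exactly on it (1/8 = 12.5%), so its bias is zero. Removals on this ground would push above the threshold; ordinary non-response need not.

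**Against a 90% line.** No target is set on the satisfaction or clarity items. If a 90% target like those in 3.2.1 were applied to the 40, it would need 36 favourable. Thirty-five of 40 misses it, and 35/39 = 89.7% still misses. With two unfavourable people unrated the base is 38, 90% of which is 34.2, so 35/38 passes.

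**Interviews.** Assume those remaining are favourable with probability 0.90 and ten are interviewed. The binomial chance of at least nine favourable is 0.736. If two of the 40 had been removed and would have been unfavourable, the rate over all 40 is 0.90 × 38/40 = 0.855, and the chance falls to 0.563.

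**After the proposed rule.** Take S = 35, r = 2, f = 2, with the two unfavourable people removed on this ground. Among rated: 33/36 = 91.7%. Over all randomised: 33/40 = 82.5% favourable; (3 + 2)/40 = 12.5% not acceptable; 2/40 = 5.0% unrated for other reasons. The reader sees all the parts.

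**The case against.** The strongest defence is that this is a welfare provision. It sits beside sustained pain and jaw locking, it is permissive, the word serious may be meant to govern the whole phrase, and 5.5.2 sends these people for clinical evaluation. Collection after removal is also partly provided for: 5.5.1 stops it only when consent is withdrawn, 6.4 asks everyone, and 6.5 adds a visit. Reasons are documented (5.5.1, 5.5.2). Removed people still appear elsewhere: all-lesson access is counted over those enrolled, and website comments can be left module by module. All of this stands. It makes a large effect less likely, but none of it guarantees a rating or says how an unrated removal counts.

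It is also fair that counting such people as not acceptable is a worst-case convention. That is why it is proposed as a second figure beside the first.

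A reader might infer more than the documents support:

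- That every acceptability percentage lacks a base. Sections 3.2.2, 3.2.3.1 and 3.2.3.2 tie the acceptability of the measures to the 80 participants, so the gap concerns program acceptability only.
- That upward bias is established. No removal rate is given, and under general non-response the bias can be zero or negative. The target "80% of participants in PACT group complete the program evaluation form" allows 8 of 40 unrated; with 35 favourable, the figure among the 32 rated could lie anywhere from 27/32 = 84.4% to 32/32 = 100%. That range reflects non-completion from any cause, not this ground.
- That open allocation makes it worse. Section 5.4.2 says "Participants and researchers are not blinded to allocation because of the nature of the study", but this adds little to a descriptive percentage.
- That the target of under 10% noting website problems would fail. Nothing equates dissatisfaction with care with reporting a website problem.

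**Conclusion.** The concern holds in limited form. A stated removal ground overlaps a primary outcome, a person removed on it before week 8 can miss both sources of program ratings, and neither 11.4 nor the SAP says how that person counts. If program acceptability is computed only among those rated or interviewed, removals on this ground can bias it upward.

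The size cannot be determined from the documents. Under the assumption of one or two unfavourable PACT participants removed and unrated, at a true 80% to 87.5%, it is about 2 to 4.6 points. That is enough to cross a 90% line in one of the illustrated starting points, if such a line applied. The conclusion rests on removals actually occurring on this ground and on those people not being rated later. It does not imply that the provision was written to improve the result.

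**What to change.** 1. In 5.5 and 5.5.2, state that dissatisfaction or confusion is a ground for termination only when it raises a safety or welfare concern, and is otherwise recorded as an acceptability finding. Since investigator discretion remains, this alone has limited effect.
2. In 6.5, set the timeframe at discontinuation. Offer the existing program evaluation and the interview invitation to discontinued participants unless consent is withdrawn.
3. In 11.4 and the SAP, report each program-acceptability percentage by arm in two ways: among those rated, and over all randomised. In the second, count unrated participants discontinued for dissatisfaction or confusion as not acceptable, and show other unrated participants as a separate count. Tabulate discontinuation reasons by arm; reasons are already logged, and the database carries group assignment (5.4.2).

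The third item matters most, because it works whichever ground is used, provided the reason is recorded. The cost is a wording amendment with IRB review (14.2), a few extra survey contacts, and acceptability figures that may come out slightly lower.

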### **5.5.1 Reasons for Withdrawal**

Study staff will record reasons for withdrawal or discontinuation when possible. If the participant withdraws consent, no further evaluations will be performed, and no attempts will be made to collect additional data.

### **5.5.2 Handling of Subject Withdrawals or Subject Discontinuation of Study Intervention**

Study staff will contact each participant who is withdrawing or discontinuation to discuss and document the reasons for withdrawal or discontinuation. All information will be documented in a log of participant completion of study activities.

Any participant discontinued due to TMD self-care practices resulting in sustained increased pain, the jaw locking, or displaying serious emotional difficulties, dissatisfaction or confusion with care during the lessons will be referred to their HealthPartners Dental Provider for further evaluation and follow-up.

